5.2 Randomization

This is an open-label trial and all participants will receive active treatment.

5.3 Remuneration

All subjects will receive:

- Parking fees paid for all in-person visits
- Lunch voucher provided for subject at each study visit that exceeds two hours, which can be used at the cafeteria at MGH CNY 149
- If appropriate, travel expenses will be reimbursed, including mileage at 58 cents per mile, up to \$150 per visit
- Honoraria: Up to \$315 if subject completes the study:
 - \$15 for the screening visit
 - \$25 for the Day 1, Day 28, and Day 84 visits (\$75 total)
 - \$100 for each lumbar puncture (x 2)
 - \$25 upon study completion

- If for any reason the subject stops the study, they will be compensated for only the visits that they have completed

Payment will be made in the form of a check mailed to the subject's home address. They should receive the check within 2-3 weeks from the date of the study visit. Their social security number (SSN) will be required in order to process the payments.

5.4 Discontinuation

5.4.1 Study Discontinuation

A study subject will be discontinued from participation in the study if:

1. Any clinical adverse event (AE), concurrent illness, or other medical condition or situation occurs such that continued participation in the study would not be in the best interest of the subject.
2. The subject meets any exclusion criteria (either newly developed or not previously recognized) and/or fails to continue to meet inclusion criteria which the study physician deems to be a risk to continued participation.

5.4.2 Discontinuation of Treatment

Individual subjects will be allowed to continue in the study, but administration of the second immunization will be withheld if, after the first injection, any of the following criteria are met:

1. Any of the following serious adverse events attributable to BCG:
 - Life-threatening adverse event
 - Permanent or severe disability
 - Important BCG-specific medical events that do not result in death, are not life-threatening, and/or do not require hospitalization will be considered as serious if, based on appropriate medical judgment, they jeopardize the participant and would require medical or surgical intervention to prevent a serious adverse event.
2. Presentations of symptoms of disseminated BCG infection including persistent fevers, night sweats, weight loss. These symptoms usually do not occur within the timeline of the current study (usually 4 months to 2 years after vaccination), however should such symptoms occur prior to the second immunization, the treatment would be stopped.
3. The occurrence of any serious local skin reactions (\geq grade 3 ulceration, abscess formation, skin necrosis at the site of vaccination, or the development of suppurative lymphadenitis) as characterized by the standard FDA Toxicity grading scale (<https://www.fda.gov/regulatory-information/search-fda-guidance-documents/toxicity-grading-scale-healthy-adult-and-adolescent-volunteers-enrolled-preventive-vaccine-clinical>).

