6 STUDY PROCEDURES

6.1 Schedule of Events

Activity	Phone Screen	Screening Visit	Baseline Visit/ BCG Vaccine 1	BCG Vaccine 2	Outcome Visit/ Early Termination	Check-In Phone
		<-28days	Day 1	Day 28 +14 days	Day 84 ±5 days	Day 98 ±5 days
Informed Consent		x				
Inclusion/Exclusion Review	x	x				
Demographics	x	x				
Create IBCID		x				
Medical History	x	x				
Concomitant Medication Review	x	x	x	x	x	x
Family History		x				
Vital Signs, Height, Weight ¹		x	x	x	x	
Physical & Neurological Exam		x				
Screening Lab Tests for Eligibility ²		x				
BCG Vaccination			x	x		
Vaccination Site Monitoring			x	x	x	
Fundoscopy					x	
Safety Lab Tests ³				x	x	
Blood Draw for Biomarkers ⁴			x	x	x	
COVID-19 Testing ⁵		x				
PT/INR		x			x	
Fasting Lumbar Puncture for Biomarkers ⁴			x		x	
MoCA and FAQ		x			x	
Cognitive/Behavioral Assessment ⁶			x		x	
Adverse Event Review		x	x	x	x	x

[1] Height and weight will be measured and recorded at the Screening visit only.

[2] Eligibility lab tests include CBC with diff, CMP, TSH, Folate, B12, HIV antibodies, serum immunoglobulins, ESR, CRP, QuantiFERON-TB Gold Test, urinalysis

[3] Safety lab tests include CBC with diff, CMP, CRP and ESR.

[4] Blood biomarkers will include PBMCs for PPD and amyloid-beta stimulation assay / flow cytometry, and serum for IIR and AD biomarkers. CSF biomarkers will be used for cytology, IIR and AD biomarkers tubes for monocyte levels of innate immunity.

[5] COVID-19 Testing includes SARS-CoV-2 PCR (nasal swab)

[6] Cognitive assessments will include RBANS, NPI-Q

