6.3.2 Physical and Neurological Examination

A physical and neurological examination will be performed at the Screening visit. The following systems will be examined: general appearance, head, eyes, ears, nose, throat, neck, chest, heart, abdomen, extremities, edema, peripheral vascular, skin and appendages, musculoskeletal, central nervous system and back.

A focused fundoscopy examination will be repeated at the outcome visit for assessment of increased intracranial pressure.

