6.3.5 Vaccination Site Monitoring

Prior to the first vaccination, both deltoids will be inspected to confirm there is no evidence of previous BCG vaccination and no obvious symptoms that would contraindicate vaccine injection. At the Day 28 visit, prior to the second injection, the vaccination site will be inspected for any signs of local infection. At the Day 84 visit and if indicated by subject-reported AEs, the site of vaccination on the arm will be examined and any visible reactivity will be recorded.

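### No lymph node check is scheduled after the first BCG dose, so an expected, recordable reaction is captured only by self-report or chance examination (minor; cheap to fix)

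*Combined protocol and SAP*

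**What the plan says.** **Withholding rule (5.4.2).** Dose 2 is withheld for "Presentations of symptoms of disseminated BCG infection including persistent fevers, night sweats, weight loss". It is also withheld for serious local reactions, among them "or the development of suppurative lymphadenitis".

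**Examination (6.3.2 and the 6.1 schedule).** "A physical and neurological examination will be performed at the Screening visit" The systems listed are "general appearance, head, eyes, ears, nose, throat, neck, chest, heart, abdomen, extremities, edema, peripheral vascular, skin and appendages, musculoskeletal, central nervous system and back". The neck is named; lymph nodes and axillae are not. The only repeat examination in that section is this: "A focused fundoscopy examination will be repeated at the outcome visit for assessment of increased intracranial pressure".

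**Site monitoring (6.3.5).** Before dose 2, "the vaccination site will be inspected for any signs of local infection". At Day 84, "the site of vaccination on the arm will be examined and any visible reactivity will be recorded". Neither sentence mentions regional nodes.

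**Weight (6.1 footnote 1 and 6.3.1.1).** "Height and weight will be measured and recorded at the Screening visit only".

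**Expected reactions and recording.** Section 9.1 lists moderate axillary or cervical lymphadenopathy among expected reactions, lasting up to 3 months. Section 11.3.1 exempts only the contained reaction at the vaccine site from adverse event status. It names two clinical routes of detection: what the participant reports and what an examination finds.

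**Other cover before dose 2.** Section 3.3.3 calls for an evaluation for systemic infection without saying what it consists of, and the 6.2.3 visit list does not itemise it. Section 6.2.3 does list vital signs (which include temperature, 6.3.1.1), safety labs (CBC with differential, CMP, CRP, ESR) and a review of history and adverse events. Section 11.3.3 adds an open question about problems or symptoms at every visit.

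**The concern.** Safety and tolerability of BCG in older adults is a stated secondary objective (3.2), and 8.1 says the findings will inform later placebo-controlled trials. Regional lymphadenopathy is one of the few reactions that 9.1 names as expected. It is often found by touch rather than by looking at the arm. With no scheduled palpation, the examination route in 11.3.1 operates for nodes only when a clinician decides to look, so ascertainment may differ between participants. No pre-dose axillary reference is specified either, although 3.3.3 grades changes from baseline.

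About half the sample is to have MCI, and the 11.3.3 question is put to the participant. Some loss through recall is plausible, though that is an inference and not a finding in the documents.

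A smaller matter is that weight loss is named as a ground for withholding dose 2, but neither a weight nor a direct question about weight loss is scheduled before that dose.

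**Working it through.** The plan states no figure on this point, so there is none to reproduce. The check compares the schedule with the criteria and then sizes the consequence.

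**1. Schedule against need**

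| Item | Why it matters | Scheduled after dose 1? |
|---|---|---|
| Suppurative lymphadenitis | withholds dose 2 (5.4.2) | site inspection only (6.3.5) |
| Ordinary axillary or cervical lymphadenopathy | expected (9.1), recordable (11.3.1) | no node check in 6.2.3, 6.2.4, 6.3.2 or 6.3.5 |
| Fever | symptom in 5.4.2 | temperature at Day 28 and Day 84 |
| Night sweats | symptom in 5.4.2 | open question only (11.3.3) |
| Weight loss | symptom in 5.4.2 | open question only; weight at Screening only |

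**2. Would existing visits fall at useful times?** Counting study days from dose 1, the outcome visit is at 84 ± 5, so 79 to 89 days after dose 1. Dose 2 is given at 28 to 42 days, so the outcome visit falls between 79 − 42 = 37 and 89 − 28 = 61 days after dose 2. Both intervals lie within the 3 months that 9.1 gives for expected lymphadenopathy. Day 84 is also the last in-person visit; Day 98 is a phone call.

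**3. Effect on the dose 2 decision.** Inputs: 0.02% rate of severe local or nodal reactions after a first vaccination (9.1), and 20 participants (3.1) or 12 (7.4 and 8.1), since the document gives both.

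- Expected cases = n × 0.0002: 12 × 0.0002 = 0.0024; 20 × 0.0002 = 0.0040.
- Chance of at least one = 1 − (1 − 0.0002)^n: 0.24% for n = 12; 0.40% for n = 20.

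The 9.1 rate pools ulcers over 1 cm, adenopathy and other skin reactions, so these are upper figures for suppurative lymphadenitis. The share that only palpation would reveal is smaller again. For the second dose, at 0.04%, the same formula gives 0.48% (n = 12) and 0.80% (n = 20), but those events come after the decision.

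**4. Age of the only scheduled weight at dose 2.** Baseline follows Screening by up to 28 days (taken as 1 to 28), and dose 2 follows by 28 to 42. The range is 1 + 28 = 29 to 28 + 42 = 70 days. This describes the gap; it does not show harm.

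**5. Ordinary lymphadenopathy.** The documents give neither a rate nor any basis for the share that self-report would miss, so the amount of under-recording cannot be calculated from them.

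**The case against.** The strongest reply is that Day 28 is already well covered. There is a required evaluation for systemic infection, a temperature, CBC, CRP and ESR, site inspection and an adverse event review. Section 9.1 describes suppurative lymphadenitis with draining sinuses, which a participant or examiner could well notice without routine palpation. Criterion 2 is a symptom rule, so history can validly trigger it, and 5.4.2 itself says disseminated symptoms usually appear 4 months to 2 years after vaccination. The trial is a single-arm, open-label, exploratory pilot with no prespecified lymphadenopathy endpoint.

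Most of this stands. It disposes of one inference a reader might draw, that the withholding rule cannot be operated or that participants are exposed to a material risk at dose 2. The documents do not support that. A Day 84 check cannot inform dose 2 at all; it serves recording only. Nor would serial weights make the rule firmer, because no weight-loss threshold exists. Day 1 and Day 84 are fasting visits while Day 28 has no fasting requirement, so those weights would not be like for like.

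What the reply does not answer is uniform recording of ordinary lymphadenopathy. Temperature and blood tests do not look for nodes, the open question depends on the participant noticing and mentioning them, and the 3.3.3 evaluation is unspecified.

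**Conclusion.** The point holds as a minor, cheap improvement. An expected and recordable reaction has no scheduled examination after dose 1, so its capture depends on self-report or on clinician initiative. The benefit is consistent safety data for the secondary objective.

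The effect on dose 2 decisions is negligible: at most about 0.24% to 0.40% for any severe local or nodal reaction after dose 1 with 12 to 20 participants, assuming the pooled 9.1 rate applies to this population.

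A reader might also infer that a definable fraction of cases will be missed, or that an upper bound on the true rate will be inflated by a known factor. That would require an assumed rate and an assumed captured share, and the documents supply neither. Palpation at fixed visits would not give complete capture either, since nodes can appear and resolve between visits. The weight element is the weaker part and supports history only.

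**What to change.** - **6.3.5:** add axillary and cervical node palpation at Day 1 (pre-dose reference, alongside the existing deltoid inspection), at Day 28 before dose 2, and at Day 84. Record it on the site-monitoring form.
- **6.2.3:** list the 3.3.3 evaluation as a step before the second vaccination, with direct questions on fever, night sweats and weight loss.
- **6.1 footnote 1 and 6.3.1.1:** allow a Day 28 weight, recorded as supporting information only.

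The withholding criteria in 5.4.2 stay as they are.

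**Cost:** a few minutes at existing visits, small form and text edits, and no extra visit. Palpation may add a few mild adverse events to the count; the Day 1 reference separates nodes already present. Sample size and analysis are unaffected.

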5.4.3 Voluntary Withdrawals

A subject may choose to discontinue participation in the study at any time. An Early Termination Visit will occur when a subject withdraws consent, i.e. withdrawing his or her participation in future study procedures.

5.4.4 Lost to follow-up

The following actions must be taken in relation to a subject who fails to attend the clinic for a required study visit:

- The site must attempt to contact the subject and re-schedule the missed visit as soon as possible.
- The site must counsel the subject on the importance of maintaining the assigned visit schedule and ascertain whether or not the subject wishes to and/or should continue in the study.

- In cases where the subject is deemed ‘lost to follow up’, the Investigator or designee must make every effort to regain contact with the subject (where possible, 3 telephone calls and if necessary a certified letter to the subject’s last known mailing address or local equivalent methods). These contact attempts should be documented in the subject’s study record.
- Should the subject continue to be unreachable, only then will he/she be considered to have withdrawn from the study with a primary reason of “Lost to Follow-up”.

5.5 Early Termination Visit (ET)

Subjects who decide to withdraw from the study at any point after receiving the initial BCG immunization will be invited to come in for an Early Termination Visit.

5.6 Termination of Study

This study may be prematurely terminated if, in the opinion of the investigator, there is sufficient reasonable cause.

Circumstances that may warrant termination include, but are not limited to:

1. Determination of unexpected, significant, or unacceptable risk to subjects;
2. Unsatisfactory enrollment;
3. Insufficient adherence to protocol requirements;
4. Data that are not sufficiently complete and/or evaluable;
5. If any grade 3 “severe” or higher adverse event occurs in three or more participants, or if participants have severe systemic reactions to the antigenicity of the vaccination with respiratory problems, the study protocol will be paused for review. The FDA, and all other relevant oversight bodies will be notified in a timely fashion if a batch of BCG is problematic. If during the study three or more subjects, representing greater than 25% of enrolled subjects, develop a systemic BCG infection in the absence of an underlying immunocompromised state, the study will be stopped for a study of this side effect.

If the study is prematurely terminated or suspended, the investigators will promptly inform the institution and regulatory authorities of the termination or suspension and the reason(s) for the termination or suspension. The IRB will also be informed promptly and provided the reason(s) for the termination or suspension by the investigator, as specified by applicable regulatory requirement(s).

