3 STUDY DESIGN

3.1 Overall Study Design and Plan

This single-site, open-label clinical trial will investigate the immune and neurobiological biomarker effects of BCG vaccination in healthy older adults and older adults with mild cognitive impairment (MCI), and gather data on tolerability, safety and study feasibility. Twenty participants (approx. n=10 cognitively normal, n=10 mild cognitive impairment) will receive two intradermal BCG vaccinations spaced 4 weeks apart and will be evaluated 12 weeks after the initial immunization. Cerebrospinal fluid (CSF) and blood will be collected at Screening (blood only), Baseline, Week 4 (blood only), and Week 12 for to assess safety, IIR and AD biomarkers.

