4.2 Recruitment

Up to twenty-six subjects will be screened and enrolled in the study, and after screening we expect twenty subjects to complete the study.

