6.2.1.3 Screen Failures

Any subject who signs consent will be considered enrolled in the study. If a subject fails screening, *at a minimum*, the following information should be captured and entered into the Electronic Data System (EDC).

- Inclusion/Exclusion Criteria
- Demographics
- Reason for screen failure

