7.4 Study Drug Preparation

The BCG vaccine is supplied as a 10-dose ampoule. For reconstitution, 1.0 ml of sterile saline is added to the 10-dose ampoule. Each 0.1ml dose is drawn by syringe from the ampoule following reconstitution and administered intradermally. Once reconstituted, the pharmacy provides the study clinic with the pre-filled syringe in a covered surgical tray to prevent light exposure. If the prepared syringe cannot be immediately administered, it will be temporarily stored at 4°C until administration (< 1 hour from reconstitution).

Each ampoule may be used for a maximum of two study participants in this pilot study of 12 participants. In this case, the ampoule will be reconstituted, and the syringes drawn at the same time. As above, the prepared syringes will be covered and stored at 4°C until administration within 1 hour of reconstitution. The remaining unused volume in the ampoule will not be used for additional patients in this pilot trial.

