8 BIOSTATISTICAL ANALYSIS

8.1 Statistical methods

This is a single-site, open-label pilot clinical trial in which twelve older adult volunteers with normal cognition or MCI will be recruited for BCG vaccination with the intent of generating preliminary descriptive data on IIR and neurobiological biomarker effects and evaluate tolerability, safety and study feasibility. No sample size calculations are performed as no prespecified comparisons are planned. Statistical analyses will describe baseline characteristics of the sample and change in biomarkers, safety and clinical measures, with pre-post paired t-tests or non-parametric equivalents (Wilcoxon sign-rank) used to evaluate within subject change. All outcomes in this pilot study are considered exploratory and no claims are attached to them, thus multiple comparison correction is not applied. A P value <0.05 will be considered significant. Findings will be used to inform the design of subsequent placebo-controlled trials of BCG vaccination for prevention and/or disease modification of Alzheimer's disease and related disorders.

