The most serious complication of BCG vaccination is disseminated BCG infection. The most frequent disseminated infection is BCG osteomyelitis (0.01 to 43 cases per million doses of vaccine administered) which usually occurs 4 months to 2 years after vaccination. Fatal disseminated BCG infection has occurred at a rate of 0.06–1.56 cases per million doses; these deaths occurred primarily among immunocompromised persons (tested for and excluded from this study).

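### The mandatory stop for systemic BCG infection uses enrolled rather than vaccinated subjects as its denominator, and its stated count of three binds only while 11 or fewer are enrolled

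*Combined protocol and SAP*

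**What the plan says.** Section 5.6 (Termination of Study) contains one clause with mandatory stopping language: "If during the study three or more subjects, representing greater than 25% of enrolled subjects, develop a systemic BCG infection" in the absence of an immunocompromised state, the study is to be stopped so that the side effect can be examined.

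The denominator is fixed by section 6.2.1.3 (Screen Failures): "Any subject who signs consent will be considered enrolled in the study".

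The protocol gives three total sizes:
- Section 3.1: "Twenty participants (approx. n=10 cognitively normal, n=10 mild cognitive impairment) will receive two intradermal BCG vaccinations".
- Section 4.2: "Up to twenty-six subjects will be screened and enrolled in the study, and after screening we expect twenty subjects to complete the study".
- Section 8.1: "twelve older adult volunteers with normal cognition or MCI will be recruited for BCG vaccination". Section 7.4 agrees with this: "Each ampoule may be used for a maximum of two study participants in this pilot study of 12 participants".

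Two other parts of the plan bear on how much the clause matters. For an individual with symptoms of disseminated infection, section 5.4.2 says that "should such symptoms occur prior to the second immunization, the treatment would be stopped". Section 9.1 describes the most frequent disseminated infection as "BCG osteomyelitis (0.01 to 43 cases per million doses of vaccine administered) which usually occurs 4 months to 2 years after vaccination".

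**The concern.** A stopping rule for a vaccine infection should have as its denominator the people who could develop it. Here the denominator also includes people who consented, failed screening and were never given BCG. They cannot contribute a case, yet each one lowers the percentage.

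The sentence also leads with a count of three, and the percentage then overrides that count over most of the planned accrual. Someone acting on the count and someone acting on the percentage would reach different decisions at 3, 4 or 5 infections among 20 enrolled. Where a stop is meant to be fixed in advance, the number should be readable without a calculation and should not depend on screening yield.

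**Working it through.** **Inputs.** Rule: at least 3 infections, and infections divided by enrolled strictly greater than 0.25 (5.6). Enrolled means all who sign consent (6.2.1.3). Stated sizes: 12 (7.4, 8.1), 20 (3.1), up to 26 (4.2). Upper documented rate: 43 per million doses (9.1). Two doses each (3.1).

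**Step 1: does three meet the rule at the stated sizes?**
- 3/12 = 25.0%, equal to 25% and not greater
- 3/20 = 15.0%
- 3/26 = 11.5%

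It does not at any of them. Three exceeds 25% only up to 11 enrolled (3/11 = 27.3%).

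**Step 2: smallest triggering count.** For N enrolled, k = max(3, floor(0.25N) + 1).

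| Enrolled (N) | Infections needed (k) |
|---|---|
| 3–11 | 3 |
| 12–15 | 4 |
| 16–19 | 5 |
| 20–23 | 6 |
| 24–26 | 7 |

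The value at 12 depends on the strict inequality. With at least 25% instead, the triggers at 12, 20 and 26 would be 3, 5 and 7.

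**Step 3: effect of screen failures.** Hold the vaccinated number at 20 and let consents rise to the section 4.2 ceiling.
- 23 consents: 6/23 = 26.1%, so 6 suffice.
- 24 consents: 6/24 = 25.0%, so 6 no longer suffice.
- 26 consents: 6/26 = 23.1% fails and 7/26 = 26.9% passes.

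Seven of 20 vaccinated is 35%. The number exposed is the same throughout.

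**Step 4: would the rule be tested at documented rates?** Twenty participants with two doses each is 40 doses. Expected cases = 43 × 10⁻⁶ × 40 = 0.00172. Per-participant risk = 1 − (1 − 43 × 10⁻⁶)² = 8.6 × 10⁻⁵. The binomial chance of 3 or more among 20 is 7.2 × 10⁻¹⁰, about 7 in 10 billion. Usual onset is 4 months or later, and the last planned contact is Day 98 (6.2.5), about 3.2 months.

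**Step 5: an unexpected hazard.** The documents give no rate for this. I assume per-participant risks of 10%, 15% and 20%. The lowest is 0.10 / (8.6 × 10⁻⁵), or about 1,160 times the documented upper rate. P(X ≥ k) is the exact binomial upper tail.

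| Assumed risk | 20 vaccinated: ≥3 | ≥6 | ≥7 | 12 vaccinated: ≥3 | ≥4 |
|---|---|---|---|---|---|
| 10% | 32% | 1% | 0.2% | 11% | 3% |
| 15% | 60% | 7% | 2% | 26% | 9% |
| 20% | 79% | 20% | 9% | 44% | 21% |

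These are final counts. They ignore the early period in which three suffices.

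**The case against.** The strongest reply is that a count floor combined with a percentage is a coherent design. The floor prevents a stop on one or two cases in a small denominator (1 of 3 is 33%, 2 of 7 is 29%), and any floor ceases to bind once the percentage demands more. The rule applies during the study. If enrolled means the running total, three does trigger the stop at 3 to 11 enrolled, a stage that every accrual passes through. Both conditions stand in one sentence, and the trigger can be worked out for any size. All of this stands.

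A reader might infer that three was the intended threshold and that the percentage is a mistake. The documents do not support that: nothing in them says that three infections should stop a study of 20, and the choice between three and 25% is not settled there.

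A reader might also infer that the study would run on unchecked through the third to fifth infections. That is not supported either. Section 5.6 lets the investigator terminate for unacceptable risk with no minimum count, and it pauses the study once three participants have events of grade 3 or higher. Section 5.4.2 withholds the second dose from an affected individual. Sections 11.3.1.1 and 11.3.6 require investigator review, IRB reporting and 24-hour entry of serious events. These layers have limits: the pause is not a stop, the documents do not say that every systemic infection would be grade 3, and withholding one person's dose does not protect those still to be vaccinated.

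The reply does not reach the denominator. Whatever number is preferred, people who never received BCG should not raise the bar for a BCG infection rule. The effect is modest: with 20 vaccinated it is one extra case, and only at 24 to 26 consents.

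**Conclusion.** The concern holds as a drafting flaw in a safety threshold, with low severity. Two things are established by arithmetic alone. The bar rises with consenting subjects who cannot develop the event (from 6 to 7 with 20 vaccinated). The stated count of three binds only up to 11 enrolled, giving triggers of 4, 6 and 7 at final sizes of 12, 20 and 26. The disagreement among those sizes is a separate matter.

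The practical consequence is small. At the highest rate in section 9.1, three cases among 20 would be expected about 7 times in 10 billion, so neither three nor six would be tested. The large contrasts under Step 5 rest wholly on assumed rates, and they apply only to a hazard that the product's record does not suggest. Section 5.6 itself contemplates a problematic batch, and that is the situation in which a clear, correctly based number would be useful.

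**What to change.** In section 5.6, replace the reference to enrolled subjects with participants who have received at least one BCG dose, and state one explicit trigger count that applies throughout accrual. The simplest wording is a stop at three or more vaccinated participants with systemic BCG infection, with the percentage removed. This is a policy choice, so the investigators and oversight bodies should confirm the number. If they prefer a higher one, it should be written as a count.

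The cost is a one-sentence amendment with no added procedures. A plain three brings a slightly higher chance of stopping. Among 20 vaccinated, P(X ≥ 3) is 0.1%, 0.7% or 7.5% at assumed true rates of 1%, 2% or 5%, all far above the documented rate.
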